#### New lesions (AK, NMSC, melanoma)

The occurrence of any new lesions (AK, NMSC, melanoma, according to AE CRF page) since screening will be summarized and tabulated according to primary system organ class and preferred term displaying the number of events as well as counts and percentages on a subject basis. Additionally, the occurrence of any new lesions will be tabulated stratified by location in relation to the treatment field (outside/inside treatment field).

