
AE: adverse event; BCC: basal cell carcinoma; BP: blood pressure; eCRF: electronic case report form; FU: follow-up; HIPAA: Health Insurance Portability and Accountability Act; HR: heart rate; NMSC: non-melanoma skin cancer; NRPS: numeric rating pain scale; PDT: photodynamic therapy; SAE: serious adverse event; SAR: serious adverse reaction; WHO: World Health Organization
 
a: Skin type will be assessed according to the Fitzpatrick rating criteria (see Appendix A)⁽¹⁾.
 
b: Clinical laboratory tests will include routine hematology, blood chemistry, and urinalysis.
 
c: AEs and concomitant medications will be assessed via phone call.
 
d: After completion of PDT cycle 1 (visit 5) .
 
e: Topical treatments within the treatment field plus a 5 cm radius surrounding the target lesion).
 
f: Local AEs in the treatment field.
 
g: Histopathological assessment to be performed according to WHO criteria⁽²⁾ in a central dermatopathological laboratory.
								
h: Only for partial or non-responders (according to clinical assessment).
 
i: Only for complete responders (according to clinical assessment).
 
k: relevant SAEs or SARs should be reported up to FU4 (60 months after start of last PDT cycle).
 
l: The time interval may be expanded after approval of the sponsor.
 
m: All female participants of childbearing potential will undergo a pregnancy test.
 
n: Only, for partial responders whose Main Target Lesion was assessed as clinically clear.
 
o: Treatment of any remaining Additional Target Lesion(s) should be carried out after final assessments and after completion of visit 8.
 
p: Only, for partial responders whose Main Target Lesion was assessed as clinically clear, esthetic appearance/outcome assessment of the Main Target Lesion should be conducted prior to its excision.
 
Unscheduled visits may be performed for safety reasons.
									

ABBREVIATIONS AND DEFINITIONS

λ_{em}	Emitted wavelength
ADE	Adverse device event
AE	Adverse event
AK	Actinic keratosis
5-ALA	5-aminolevulinic acid
ALT (SGPT)	Alanine aminotransferase
AP	Alkaline phosphatase
AST (SGOT)	Aspartate aminotransferase
ATC	Anatomical Therapeutic Chemical Classification System
BCC	Basal cell carcinoma
BD	Bowen's disease/ squamous cell carcinoma (SCC) in situ
BF-200 ALA	Nanoemulsion gel formulation containing 7.8% ALA (development name for Ameluz®)
BMI	Body mass index
BP	Blood pressure
cm	centimeter(s)

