4.4 EXCLUSION CRITERIA

Subjects presenting with any of the following criteria will not be included in the study:

- History of hypersensitivity to 5-ALA or any ingredient of BF-200 ALA which includes soybean phosphatidylcholine.
- Hypersensitivity to porphyrins.
- Current treatment with immunosuppression therapy.
- Presence of photodermatoses.
- Presence of porphyria.
- Presence of clinically significant inherited or acquired coagulation defect.
- Evidence of clinically significant (CS) unstable medical conditions, such as:

- Metastatic tumor or tumor with high probability of metastasis.
 - Cardiovascular disease class III, IV (New York Heart Association [NYHA]).
 - Immunosuppressive condition.
 - Hematologic, hepatic, renal, neurologic, or endocrine condition.
 - Collagen-vascular condition.
 - Gastrointestinal condition.
- Clinically relevant cardiovascular, hepatic, renal, neurologic, endocrine, or other major systemic diseases that complicate implementation of the protocol or interpretation of the study results.
- Gorlin Syndrome or Xeroderma pigmentosum.
- Presence and/or physical treatment of skin tumors other than (naïve) sBCC (e.g. malignant melanoma, squamous cell carcinoma (SCC), Bowen's disease, aggressive BCC or nBCC diagnosed at the screening visit by clinical assessment) within a distance of \leq 5 cm from the nearest target lesion within 4 weeks prior to PDT (Visit 2) until the end of the clinical observation period. However, biopsied lesion(s) that were not confirmed eligible at screening and which are located at a distance of $>$ 5 cm from any lesion(s) that will be included in the study can be surgically removed. Treatment by PDT or topical medication during the course of the clinical observation period of the study triggers exclusion of the subject.
- If lesion(s) are assessed as non-eligible by biopsy during initial screening and these lesions are localized within a distance of 5 cm from an otherwise suitable lesion, this suitable lesion must be excluded from the study.
- Any AK lesions within the treatment field (lesion area including margin of 0.5 to 1.0 cm).
- Any topical medical treatment of AK, other non-melanoma skin cancers (NMSC), or melanoma (except for IMP treatment of target lesion(s)) starting 12 weeks prior to Visit 2 (PDT-1) and lasting until the end of the clinical observation period.

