4.5 SCREENING FAILURES

All subjects that match one or both of the following criteria prior to IMP application will be considered as screening failures:

- They do not meet one or more inclusion criteria.
- They meet one or more exclusion criteria.

Subjects assessed as screening failures will not be randomized at Visit 2. Hence, they will be considered as dropouts that do not contribute to the Randomized set.

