- Double check all inclusion and exclusion criteria, in particular the confirmation of diagnosis of sBCC for at least one lesion based on the result of the histopathological evaluation. The subject must not be randomized if no lesion fulfills the criteria or if all eligible lesions are located closer than 5 cm to one of the non-suitable BCC lesions.
- Randomization and assignment of randomization number.
- Assessment of the sBCC lesion(s) (lesion count, location, and size).
- Measurement of vital signs (HR and BP).
- Pregnancy test (urine) for females of reproductive potential.

- Definition of the Main Target Lesion and application of at least 3 ink marks to establish its exact position. Further lesions included in the study will be regarded as Additional Target Lesions. The Main Target Lesion should be representative for the eligible lesions of the subject and should take the burden for the subject into account. However, for the Main Target Lesion, the maximal lesion size should be such that surgical excision without a skin transplant is feasible according to the investigator's judgement. In cases where two or more lesions would qualify as Main Target Lesion, the lesion whose excision will cause the least burden for the subject shall be selected. (Please refer also to *Definition of Target Lesions, illumination and treatment region*, [Section 7.3.1](#))
- Thorough preparation of eligible lesions and application of IMP (see [Section 5.1.2](#)).
- Documentation of time of IMP application and removal.
- All target lesion(s) will be illuminated with BF-RhodoLED® until a total light dose of 37 J/cm² per treatment field is achieved. In cases of severe pain, illumination may be shortly interrupted, e.g. to inject a fast acting local anesthetic, such as xylocaine (see [Section 5.1.3](#)).
- Documentation of illumination procedures, including time of illumination (10 min) and distance of the LED lamp to the treated lesion(s) (5-8 cm). Additional documentation of possible pain induced interruptions (duration, frequency) and pain relieving measures during illumination. Deviations from the standard illumination procedure have to be justified.
- Pain reported by the subject during the illumination will be recorded using the numeric rating pain scale (NRPS) by the provided subject's pain questionnaire (see [Section 7.3.2](#)).

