- Discomfort reported by the subject during the illumination will be recorded by the provided subject's discomfort questionnaire (see [Section 7.3.2](#)).
- Documentation of AEs, including local skin reactions, local discomfort, and pain during and/or after PDT at the treatment field(s).
- Documentation of new AK, NMSC and melanoma, including location of lesion(s).
- Documentation of concomitant medications/treatments including those, which might be taken for pain management during and/or after PDT.
- Subject should be reminded about allowed and forbidden medications (see [Visit 1](#)).
- Investigator will send a subject status confirmation by FAX or email.

Visit 3, PDT-2 (1-2 weeks post PDT-1 (Visit 2))

- Assessment of how the subject is feeling since last PDT. Using non-leading questions such as "How did you feel since your photodynamic treatment session", the investigator or delegated person will evaluate any discomfort the subject may be experiencing. Any reported AE or concomitant treatment will be documented.
- Measurement of vital signs (HR and BP).
- Pregnancy test (urine) for females of reproductive potential.
- Thorough preparation of the treated BCC target lesion(s) and application of IMP (see [Section 5.1.2](#)).
- Documentation of time of IMP application and removal.

- The target lesion(s) will be illuminated with an LED lamp (BF-RhodoLED®) until a total light dose of 37 J/cm² (per treatment field) is achieved. In cases of severe pain, illumination may be shortly interrupted, e.g. to inject a fast acting local-anesthetic, such as xylocaine (see [Section 5.1.3](#)).
- Documentation of illumination procedures, including time of illumination (10 min) and distance of the LED lamp to the treated lesion(s) (5-8 cm). Additional documentation of possible pain induced interruptions (duration, frequency) and pain relieving measures during illumination. Deviations from the standard illumination procedure have to be justified.
- Pain reported by the subject during the illumination will be recorded using the NRPS by the provided subject's pain questionnaire (see [Section 7.3.2](#)).
- Discomfort reported by the subject during the illumination will be recorded by the provided subject's discomfort questionnaire (see [Section 7.3.2](#)).
- Documentation of AEs, including local skin reactions, local discomfort, and pain during and/or after PDT at the treatment field(s).
- Documentation of new AK, NMSC and melanoma, including location of lesion(s).

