8.2 PERIOD OF OBSERVATION

For the purposes of this study, the period of observation for collection of AEs extends from the time the subject gives informed consent until the end of the clinical observation period of the study at Visit 5 or Visit 8 (in case of re-treatment with a 2nd PDT cycle).

At the FU visits, any local AEs (i.e., AEs affecting skin health in the treatment fields), which might impair proper assessment of the recurrence of the treated sBCC lesions, or other clinically relevant

events at the investigator's discretion, or conditions that may be relevant for proper assessment of the recurrence of the treated BCC lesions) should be documented including any recurrent BCC lesions and any new lesions (AK, other NMSC, and melanoma) (see [Section 7.2.3](#)).

Relevant SAEs or related SAEs (SARs) should be documented until the end of the FU period (60 months after completion of the 1st PDT cycle (Visit 5)).

If the investigators detect an SAE in a subject after the end of the FU period, and considers the event possibly related to prior study treatment or procedures, they should report this event to the pharmacovigilance department of the sponsor.

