11.3.4 Safety analyses

All secondary safety endpoints (see [Section 7.3.2](#) and [Section 11.1.6](#)) will be analyzed descriptively and in an exploratory way. These safety analyses will be performed for the SAF set.

AEs will be coded according to the latest Medical Dictionary for Regulatory Activities (MedDRA) version available at the day of database closure. The analysis will focus on the TEAEs. TEAEs will be summarized and tabulated according to primary system organ class and preferred term. TEAEs leading to death and TEAEs resulting in discontinuation of study will be tabulated using frequency tables if a reasonable number of AEs of this type are observed. The occurrence of any new lesions by type (AK, NMSC, and melanoma) will be tabulated using frequency tables.

A listing of subjects with AEs will be provided for all AEs reported and all subjects enrolled.

The frequency of local skin reactions at the treatment field and of local discomfort will be presented together with the respective CIs for each treatment group. The mean and the maximal pain score and the respective CIs will be presented for each assessment time point and treatment group.

All laboratory values will be classified as normal or abnormal according to the laboratory's normal ranges and indicated as CS or NCS by the investigator. Out of range laboratory values that are considered CS will be documented in the medical history (Visit 1) or as AEs (Visit 5 or Visit 8) and listed as such. Details of further analyses will be specified in the SAP.

The analyses of variables for vital signs will focus on the evaluation of the change from baseline to the scheduled time points after baseline. Descriptive analysis (number of subjects, mean, median and SD, minimum, maximum) of the time course and of changes from baseline to each post-baseline time point will be presented.

General physical examinations will include the following body systems: heart, lung, abdomen, nervous system, skin, musculoskeletal system, lymph nodes, limbs, head, ears, eyes, nose, throat, and others. All clinically significant abnormal physical findings will be listed. Details of further analyses will be specified in the SAP.

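### The SAP's new-lesion table starts at screening and has no split at PDT-1, so its total and outside-field rows mix lesions recorded before treatment with later ones

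*SAP*

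**What the plan says.** SAP 4.5, under new lesions, states: "The occurrence of any new lesions (AK, NMSC, melanoma, according to AE CRF page) since screening will be summarized and tabulated". The table is arranged by system organ class and preferred term, with an added split by position inside or outside the treatment field. Protocol 11.3.4 is less specific: "The occurrence of any new lesions by type (AK, NMSC, and melanoma) will be tabulated using frequency tables".

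Pre-treatment lesions can reach this table. Protocol 7.3.2 has new lesions reported as adverse events, and under Protocol 8.2 "the period of observation for collection of AEs extends from the time the subject gives informed consent". Existing lesions are recorded at Visit 1. At Visit 2, the PDT-1 visit, Protocol 7.2.1 requires "Documentation of new AK, NMSC and melanoma, including location of lesion(s". Visit 1 may be up to 4 weeks before PDT-1, and a footnote to Table 1 adds: "The time interval may be expanded after approval of the sponsor". SAP section 4 removes adverse events that start after the clinical phase ends but sets no lower limit at treatment.

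Elsewhere in SAP 4.5, treatment-emergent events and local reactions are both timed from treatment.

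**The concern.** New AK, NMSC and melanoma are a named safety variable (Protocol 11.1.6). A reader will naturally look to this table for how often new lesions appeared after treatment began. Randomization takes place at Visit 2, so a lesion that appeared between Visit 1 and PDT-1 preceded both assignment and exposure and says nothing about either arm. If the total and outside-field rows are read as incidence on study treatment, they are too high.

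No other table described in the SAP body supplies the missing count. The treatment-emergent table starts at the right point but closes 28 days after the last PDT of each cycle, except for events judged at least possibly related. The all-event table again includes onsets before treatment.

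**Working it through.** The plan states no figure on this point, so there is none to reproduce. The check compares counting windows.

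**Which rows are exposed.** Protocol 4.4 excludes "Any AK lesions within the treatment field (lesion area including margin of 0.5 to 1.0 cm", and also excludes skin tumours other than naive sBCC within 5 cm of a target lesion. At Visit 2 the site must "Double check all inclusion and exclusion criteria", and Protocol 4.5 adds: "All subjects that match one or both of the following criteria prior to IMP application will be considered as screening failures". The inside-field row is therefore largely protected. What remains is AK outside the field, tumours more than 5 cm away and new naive sBCC, which fall mainly in the outside-field and total rows.

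**Pre-treatment share of the window.** Inputs:
- g = weeks from Visit 1 to PDT-1: up to 4 in the protocol. The value 6 is my assumption for an extended screening period.
- w = weeks from PDT-1 to the end of the clinical phase: 12 or 24 (Protocol 3.2).

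Share = g/(g + w):

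| g | w = 12 (ends at Visit 5) | w = 24 (retreated) |
|---|---|---|
| 2 | 2/14 = 14% | 2/26 = 8% |
| 4 | 4/16 = 25% | 4/28 = 14% |
| 6 (assumed) | 6/18 = 33% | 6/30 = 20% |

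These are shares of time. They become shares of lesions only if lesions are recorded at a constant rate, and the documents give no new-lesion rate.

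**What the treatment-emergent table covers.** PDTs within a cycle are 7 to 14 days apart and the window runs 28 days past the last one. Coverage per 84-day cycle is (7 + 28)/84 = 42% to (14 + 28)/84 = 50%. For the other 50% to 58% of each cycle, a lesion judged unrelated or unlikely related is left out of that table. The SAP sends it to the non-treatment-emergent listing, which also holds pre-treatment events. That listing gives a start day relative to treatment only when the date is complete.

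**Effect on the arm comparison.** Subjects stop at 12 or 24 weeks according to clinical response, so vehicle subjects are probably followed longer. Retreatment rates are not given. I assume 20% to 50% for BF-200 ALA and 60% to 90% for vehicle. Mean follow-up after PDT-1 = 12 + 12 × (retreated proportion):
- BF-200 ALA: 14.4 to 18.0 weeks
- Vehicle: 19.2 to 22.8 weeks

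With a constant and equal true lesion rate in both arms, the ratio of events per subject (BF-200 ALA to vehicle) is:
- counted from PDT-1: 14.4/22.8 = 0.63 to 18.0/19.2 = 0.94
- counted from screening with g = 4: 18.4/26.8 = 0.69 to 22.0/23.2 = 0.95

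Neither raw count shows 1.0 when the true ratio is 1.0. Moving the start to PDT-1 takes the raw ratio slightly further from 1, so a split at PDT-1 needs a follow-up adjustment beside it.

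**The case against.** The strongest reply is that the table does what the protocol asks. Protocol 11.1.6 makes new lesions a variable of the clinical observation period. The synopsis and Protocol 3.1 describe that period as including the screening visit and the weeks before randomization, and SAP section 1 repeats this. Protocol 3.1 also uses the term more narrowly, but starting at screening is a faithful reading and the start is openly stated. This stands. A reader might infer that the SAP departed from the protocol; the documents do not support that.

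A second reply is that the effect is small. Safety is descriptive, the inside-field row, where a local effect is most plausible, is largely protected, and nothing in the documents suggests a treatment effect outside the field. Table 1 first schedules the new-lesion check at Visit 2, so pre-treatment recording comes chiefly from one inspection on the PDT-1 day. This also stands and limits the point to a minor one.

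A third is that the data are not lost. Later lesions judged related stay in the treatment-emergent table, and the others can be traced in listings. That is true, but the reader would have to rebuild the count by hand, and only where start dates are complete.

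Finally, Appendix A of the SAP sets the table variables and may already contain the split. If so, nothing needs changing.

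**Conclusion.** The point holds as a low-cost improvement to one descriptive table. In the SAP body, the total and outside-field rows pool lesions recorded before randomization and treatment with later ones, and no described table gives all new lesions from PDT-1 to Visit 5 or Visit 8. Within the unextended 4-week limit, pre-treatment time is at most about 25% of the window for subjects ending at Visit 5 and 14% for retreated subjects. Reading those shares as lesion counts requires a constant recording rate.

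Two further inferences should be resisted. One is that pooling is harmless under no effect because randomization balances pre-treatment lesions: that balance is expected for the screening weeks, but later follow-up depends on response, so a true ratio of 1.0 need not appear as 1.0. The other is that restricting the table to onset after PDT-1 gives a clean arm comparison by itself; under the assumed retreatment rates it does not. No confirmatory test, alpha level or efficacy result is touched.

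**What to change.** In SAP 4.5, keep the total counted from screening and add rows by arm and by inside/outside the treatment field for:
- onset before first IMP application, including lesions found at Visit 2 before application;
- onset from first IMP application through Visit 5 or Visit 8, without the 28-day limit.

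Because follow-up length depends on response, also give the post-treatment count for the window common to all subjects, up to Visit 5, or per person-time.

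The cost is a short SAP addition, a date filter with the extra rows, and one further summary for the common window or person-time; no protocol change is needed. The post-treatment row will hold fewer events than the total. Recorded onset is largely the date of detection, so a lesion missed before PDT-1 and first seen afterwards will still count as post-treatment.

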#### Local discomfort

The frequency and exact 95% CIs for each proportion of local discomfort during PDT (illumination) (using a 4-point scale ranging from none (0) to severe (3) for each category: burning, itching, other) will be presented by category and for each assessment time point. Local discomfort per illumination field, i.e. per lesion location (body system) as well, is available. Worst intensity over all timepoints for each lesion location and category will be considered for tabulation. In case of both illumination fields have same location, worst intensity of both illumination fields will be considered for tabulation. Missing or unknown intensity will not be considered for worst intensity analysis. Additionally, binary variables for each lesion location and category will be created for presentation of 95% CIs. Variable will be 'yes' if corresponding discomfort is documented at least once over all timepoints for corresponding lesion location. Otherwise, variable will be 'no'. In case of both illumination fields have same location fields have same location, variable will be 'yes' if corresponding discomfort is documented at least once over all timepoints for corresponding lesion location. Otherwise, variable will be 'no'.

#### Pain

Pain reported during PDT (illumination) will be assessed using an 11-point numeric rating pain scale (NRPS) assessment by the subject. Pain assessment per illumination field, i.e. per lesion location (body system) as well, is available. The mean pain score with exact 95% CIs will be presented for each assessment time point and lesion location. In case of both illumination fields have same location, pain of both illumination fields will be considered for tabulation. Additionally, mean of the maximum pain score (worst intensity) over all timepoints with exact 95% CIs for each lesion location will be presented. In case of both illumination fields have same location, maximum pain score (worst intensity) of both illumination fields will be considered for tabulation.

